## 3.0 PARTICIPANT SELECTION

### 3.1 Inclusion Criteria

A participant must meet all of the following criteria to be eligible for enrollment.

- 3.1.1** Histologically confirmed diagnosis of multiple myeloma with a measurable disease parameter at time of screening. A measurable disease parameter is defined as one or more of the following:
- Serum monoclonal protein  $\geq 0.5$  g/dl.
  - 24 hour urine monoclonal protein  $\geq 0.2$  g/24 hour
  - Serum free light chain ratio  $> 5x$  normal ratio with an absolute difference of 10mg/dl between the involved and uninvolved free light chain.
  - Soft tissue plasmacytoma  $\geq 2$  cm measurable by either physical examination and/or applicable radiographs (e.g. MRI, CT, etc).
  - Bone Marrow Plasma Cells  $\geq 30\%$ .
- 3.1.2** Documentation of at least one line of prior myeloma therapy now with relapsed or refractory disease requiring re-treatment.
- 3.1.3**  $\geq 18$  years of age at time of signing the informed consent.

*Note:* No dosing or adverse event data are currently available on the use of carfilzomib in combination with PLD in participants  $< 18$  years of age. Thus, children and adolescents are excluded from this study but will be eligible for future pediatric phase 2 combination trials.

- 3.1.4** Performance status of ECOG  $\leq 2$  or Karnofsky  $\geq 60$  % (see Appendix A and B).

*Note:* Participants with lower performance status based solely on bone pain secondary to multiple myeloma will be eligible.

- 3.1.5** Required Laboratory Values
- ALT (SGPT) and AST (SGOT)  $< 2.5$  x the upper limit of the institutional normal value (ULN).
  - Total bilirubin  $\leq 1.5$  x ULN.
  - ANC  $\geq 1,000$ .
  - Hemoglobin  $\geq 8$  g/dl.
  - Platelets  $\geq 50,000$ .
  - Creatinine clearance  $> 15$  ml/minute using Cockcroft-Gault formula (See Appendix C).
  - For those participants receiving warfarin (Coumadin), unfractionated heparin, or low-molecular weight heparin therapy, the applicable

coagulation parameter that is being monitored must be within the accepted therapeutic ranges for those indications.

*Note:* Transfusions and/or growth factor dependent participants are not excluded if the above parameters can be achieved with such support.

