## 9.5 Partial Response

Partial response (PR) requires all of the following:

- $\geq 50\%$  reduction in the level of the serum monoclonal protein for at least two determinations performed a minimum of six weeks apart.
- Reduction in urine monoclonal protein by either  $\geq 90\%$  or to  $\leq 200$  mg for at least two determinations performed a minimum of six weeks apart.
- If present,  $\geq 50\%$  reduction in the size of soft tissue plasmacytomas (by clinical or radiographic examinations) for at least six weeks.
- If serum and urine monoclonal protein are unmeasurable, a  $\geq 50\%$  decrease in difference between the involved and uninvolved free light chain levels is required in place of monoclonal protein criteria (The absolute decrease must

- be  $\geq 10$  mg/dl)
- If serum and urine monoclonal protein are unmeasurable and serum free light chain is unmeasurable, a  $\geq 50\%$  reduction in plasma cells is required in place of monoclonal protein provided that baseline bone marrow plasma cell percentage was  $\geq 30\%$

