## 9.6 Minimal Response

Minimal response (MR) requires all of the following:

- $\geq 25\%$  to  $< 49\%$  reduction in the level of serum monoclonal protein for at least two determinations six weeks apart.
- If present, a 50 to 89% reduction in 24-hour urine monoclonal protein which still exceeds 200 mg/24hr, for at least two determinations six weeks apart.
- 25-49% reduction in the size of plasmacytomas (by clinical or radiographic examinations) for at least six weeks.
- No increase in size or number of lytic bone lesions (development of compression fracture does not exclude response).

*Note:* MR includes participants in whom some but not all criteria for PR are fulfilled providing the remaining criteria satisfy the requirements for MR.

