h: All participants must complete 24 hour urine at screening and for confirmation of CR or VGPR if necessary. Additional serial 24-hour urines only required for participants with  $\geq 0.2g/24$  hours of monoclonal protein at screening.

j: Required only in women of childbearing potential; 2 negative test results required before study drug dosing on Cycle 1 Day 1.

k: Only required if clinically indicated. Imaging can include X-ray, CT, MRI, PET, etc.

m: To be repeated on study when clinically indicated.

n: Bone marrow aspirate and core biopsy for differential, cytogenetics, and fluorescent *in situ* hybridization (FISH) studies. To be repeated on study for confirmation of CR or sCR.

o: To be repeated on study whenever a bone marrow biopsy and aspirate is performed.

p: Only for patients treated in part 2 of phase 1 or phase 2.

1: Not required to be repeated in Cycle 1 if screening assessment was within 7 days of Day 1.

2: Only during Cycle 1.

3: Optional. If patient is willing and able.

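### Section 9.5 makes PR depend on two urine M-protein values that the study calendar does not require when screening urine is below 0.2 g/24 h, so some serum responders are non-successes on a literal reading

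*Combined protocol and SAP*

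**What the plan says.** **Response definition.** Section 9.5 opens with "Partial response (PR) requires all of the following". Its first bullet is a serum M-protein fall of at least 50%. Its second is a "Reduction in urine monoclonal protein by either" at least 90% or to 200 mg or less, "for at least two determinations performed a minimum of six weeks apart". The urine bullet has no condition attached. The plasmacytoma bullet in the same list applies only if such a lesion is present, and the MR urine bullet in Section 9.6 begins "If present, a 50 to 89% reduction in 24-hour urine monoclonal protein". Section 9.5 offers substitutes (free light chains, then marrow plasma cells), introduced by "If serum and urine monoclonal protein are unmeasurable, a". They need both components to be unmeasurable.

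**Assessment schedule.** The calendar in Section 10.0 has a 24-hour urine row marked at screening and on Day 1 of cycles, but footnote h limits it: "All participants must complete 24 hour urine at screening and for confirmation of CR or VGPR if necessary". It continues: "Additional serial 24-hour urines only required for participants with" 0.2 g/24 h or more of monoclonal protein at screening. PR is not mentioned.

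**Eligibility.** Section 3.1.1 states: "A measurable disease parameter is defined as one or more of the following". Serum M-protein of 0.5 g/dl or more is enough alone, so a participant with little or no urine protein is eligible.

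**Endpoint.** Section 15.1 counts CR, VGPR and PR as responses. MR and SD do not count.

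**The concern.** PR is the lowest category that counts as a success, so its boundary decides the primary endpoint for anyone whose best response is partial. The definition asks for urine data that the calendar does not require from a group the protocol admits by design: participants followed on serum protein, with low urine protein at screening.

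A site that follows the calendar exactly will reach response assessment for such a participant without the urine values. Either the participant is scored MR or SD despite a confirmed serum response, or the assessor treats the urine bullet as satisfied or not applicable, on a rule that is not written down. Phase II is judged by a fixed count of successes in a small sample, so a few participants classified one way or the other can change the conclusion.

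**Working it through.** **Step 1. Values needed against values required.** Take a participant with serum M-protein of at least 0.5 g/dl, screening urine M-protein below 0.2 g/24 h, and a confirmed serum fall of at least 50% that does not reach VGPR.

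- Urine determinations needed by Section 9.5: at least 2, six or more weeks apart.
- On-treatment 24-hour urines required by footnote h: 0. The serial requirement starts at 0.2 g/24 h, and CR or VGPR is not being confirmed.
- If the screening value is counted: 1 of 2. It is also a baseline value, so it cannot show a reduction.
- Substitution by light chains or marrow: not available, because serum is measurable.

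**Step 2. Where the participant falls.** The note in Section 9.6 places a participant who meets some but not all PR criteria in MR, if the remaining criteria satisfy MR. Otherwise Section 9.7 makes it SD. Neither is a success under Section 15.1.

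**Step 3. The phase II rules before any loss.** The plan gives two rules: 24 participants with 8 or more successes (Section 16.0), and 17 participants with 5 or fewer meaning ineffective, so 6 or more to pass (Section 5.3). That difference is a separate matter, and both are carried here. The null is 20% and the alternative 40% (Section 16.0). With X binomial,

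P(X ≥ r) = Σ from k = r to n of C(n,k) p^k (1−p)^(n−k).

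- 8 of 24: 0.0892 at p = 0.20; 0.808 at p = 0.40.
- 6 of 17: 0.1057 at p = 0.20; 0.736 at p = 0.40.

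Section 16.0 states a significance level of 0.10, which the 24-participant rule meets as a ceiling and the 17-participant rule slightly exceeds. It states no power figure.

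**Step 4. Power under strict literal scoring.** Let q be the share of true responders who are PR-level, had screening urine below 0.2 g/24 h, and have no later pair of urine values. **The documents do not give q; it is assumed.** The success probability becomes p = 0.40 × (1 − q).

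| q | p | 8 or more of 24 | 6 or more of 17 |
|---|---|---|---|
| 0 | 0.40 | 0.808 | 0.736 |
| 5% | 0.38 | 0.749 | 0.678 |
| 10% | 0.36 | 0.680 | 0.614 |
| 20% | 0.32 | 0.521 | 0.475 |

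At q = 10% the loss is 0.808 − 0.680 = 0.128 for the 24-participant rule and 0.736 − 0.614 = 0.122 for the 17-participant rule. Strict scoring can only remove successes, so it pushes towards declaring the regimen ineffective.

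**Step 5. The mirror case.** The serum bullet in Section 9.5 is also unconditional. A participant who enters on urine protein alone, with serum M-protein too low to measure, cannot readily show a 50% serum fall, and the substitution does not apply because urine is measurable.

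**The case against.** The best counter-argument is that the thresholds coincide. Footnote h stops serial urines below 0.2 g/24 h, which is the same 200 mg that satisfies the second limb of the PR bullet. A participant released from serial collection already sits under that limit. Footnote h keeps urine for CR and VGPR, where it could still change the category: VGPR by the serum-reduction route needs urine below 100 mg, and CR needs negative urine immunofixation. On this view urine is collected where it matters and skipped where the PR limit is already met. The contrast with Section 9.6 is also weaker than it looks. The MR bullet requires urine protein still above 200 mg, so it needs its qualifier more than the PR bullet does.

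This reading is plausible and probably what was intended. It would also be one uniform rule, not a case-by-case waiver. What it lacks is any statement in the protocol, and it conflicts with the words that are there: one screening value is neither a reduction nor two determinations.

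Three stronger inferences are tempting and should not be drawn:

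- That every participant needs urine values for PR. Those with neither serum nor urine measurable move to light chains or marrow.
- That no urine will be collected. Footnote h says what is required and forbids nothing; a site may collect more, and urine taken to confirm CR or VGPR could also serve for PR.
- That these responders can never be scored PR. That follows only if the bullet is applied literally and no extra urine exists.

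**Conclusion.** The point stands as a gap between the PR definition and the schedule that feeds it. For a participant with measurable serum protein and screening urine below 0.2 g/24 h whose best response is PR, the protocol requires none of the two urine values that Section 9.5 demands. The literal result is a non-success in the primary endpoint.

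The size cannot be fixed from the documents. The power losses hold only if assessors score strictly and literally, and only for the assumed q: about 6 percentage points at 5%, 12 to 13 at 10%, and 26 to 29 at 20%, across the two rules. If assessors uniformly treat a low screening value as meeting the bullet, q is effectively zero and no power is lost. The table therefore shows what the ambiguity could cost; it does not predict what will happen. The case for changing the text is that a primary-endpoint category should not rest on an unwritten reading when the protocol already contains the threshold that would settle it.

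**What to change.** Make each M-protein bullet in Section 9.5 conditional on that component being measurable at screening, with the thresholds in Section 3.1.1. For example: *if serum M-protein was 0.5 g/dl or more at screening*, before the serum bullet; and *if urine M-protein was 0.2 g/24 h or more at screening*, before the urine bullet. The urine threshold is the one footnote h already uses, so definition and calendar then agree. Conditioning both bullets also closes the mirror gap for participants followed on urine alone; changing only the urine bullet would leave it open.

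The cost is two short clauses and no added visits or samples. The downside is negligible: urine is still required to confirm CR and VGPR, and serum free light chains remain scheduled every cycle. Adding PR confirmation to footnote h would also close the urine gap, but it adds collections and leaves the serum bullet as it is. Whichever is chosen should be in place before responses are assessed for the primary endpoint.

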## 10.0 STUDY CALENDAR

Assessment *	Screening a	Cycles 1 through 6						Cycles 7 and beyond				End of Study b	Follow-up c	
		D1	D2	D8	D9	D15	D16	D1	D8	D15	D22			
Sign informed consent	X													
Medical & treatment history	X													
Vital signs d	X	X	X	X	X	X	X	X	X	X	X	X		
Physical exam e	X	X 						X						
Toxicity assessment	X	X	X	X	X	X	X	X	X	X	X	X	X	
CBC w/ differential	X	X		X		X		X	X	X	X	X	X	
Chemistries f	X	X	X	X	X	X	X	X	X	X	X	X	X	
PT/INR & PTT	X	X 												
SPEP & IFIX g	X	X 				X 		X					X	
24-hour urine total protein, UPEP, & IFIX gh	X	X 				X 		X					X	
Serum free light chains	X	X 				X 		X					X	
Quantitative immunoglobulins (IgA, IgG, IgM)	X	X 				X 		X					X	
Beta-2 microglobulin	X	X 						X					X	
Serum $\beta$ HCG j	X	X						X					X	
EKG & Chest x-ray	X													
MUGA or Echo m	X													
Imaging for plasmacytoma assessment km	X												X 	
Skeletal survey m	X												X 	
Bone marrow biopsy & aspirate n	X												X 	
Correlative samples o	X												X 	
Carfilzomib administration		X	X	X	X	X	X	X	X	X	X	X		
PLD administration				X										
Dexamethasone administration p		X	X	X	X	X	X	X	X	X	X	X		
Follow-up for survival														X

\* All assessments allowed a window of +/- 2 days for scheduling issues (such as holidays)

a: Screening period is D-21 though D1 prior to Carfilzomib dose

b: End of study must be within 30 days of last dose of study drug

c: Follow-up takes place every 3 months for up to 18 months or until resolution or stabilization of adverse events, whichever is longer

d: To be done within 1 hour prior to carfilzomib administration.

e: Physical exam includes height, weight, BSA, performance status, neurological assessment and plasmacytoma assessment if indicated .

f: Chemistries include Complete Metabolic Panel with Renal and Hepatic Panels, LDH, Magnesium, Phosphorous, Uric Acid.

g: SPEP = serum protein electrophoresis, IFIX=immunofixation, UPEP= urine protein electrophoresis.

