### **15.0 ENDPOINTS**

#### **15.1 Primary Outcome Analyses**

The primary endpoint for each arm of the phase II portion of this trial is the proportion of confirmed tumor responses. A confirmed response is defined to be a CR, VGPR, or PR noted as the objective status. Response will be evaluated using up to 12 cycles of treatment. All participants meeting the eligibility criteria who have signed a consent form and have begun treatment will be evaluable for response.

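### Partial response by the light-chain substitute carries no repeat requirement, so on the literal text one qualifying fall counts as a confirmed primary-endpoint success

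*Combined protocol and SAP*

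**What the plan says.** Section 9.5 lists what a partial response requires.

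- **Serum M-protein:** a 50% "reduction in the level of the serum monoclonal protein for at least two determinations performed a minimum of six weeks apart".
- **Urine M-protein:** its own reduction, again "for at least two determinations performed a minimum of six weeks apart".
- **Plasmacytoma, if present:** a 50% "reduction in the size of soft tissue plasmacytomas (by clinical or radiographic examinations) for at least six weeks".
- **Light chains, if serum and urine M-protein are unmeasurable:** a 50% "decrease in difference between the involved and uninvolved free light chain levels is required in place of monoclonal protein criteria", with an absolute fall of at least 10 mg/dl. No repeat and no interval are stated.

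Under section 15.1 the phase II primary endpoint "is the proportion of confirmed tumor responses". The same section explains the term: "A confirmed response is defined to be a CR, VGPR, or PR noted as the objective status". Response is assessed over up to 12 cycles.

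Section 3.1.1 admits participants who are measurable by light chains alone. Section 10.0 schedules "Serum free light chains" at screening, on Day 1 of each cycle and on Day 15 of Cycle 1.

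**The concern.** The repeat requirement is written inside the serum and urine bullets. The light-chain criterion replaces those bullets, so on the plain wording the repeat requirement goes with them. Section 15.1 does not restore it, because it adds no confirmation step and takes whatever section 9 yields. Most participants would then be scored on a sustained fall, while those on the light-chain route would be scored on whether any single on-treatment value ever qualified.

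The phase II decision compares a count of successes with a fixed cut-off. One transient fall scored as a success moves that count by one, and the result comes to depend on the mix of disease types enrolled. Two assessors could also score the same participant differently, according to whether each carries the repeat requirement over.

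**Working it through.** **1. The text.** The light-chain bullet has no repeat clause of its own, and neither section 9.5 nor section 15.1 has a general clause covering all routes. Section 9.8 shows the same pattern for progression: a repeat investigation is required for serum and urine M-protein and is not mentioned for light chains. Complete response (9.1) and very good partial response (9.4) have their own two-determination rules and no light-chain substitute, so the gap affects partial response only.

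**2. The plan's own figure.** Section 16.0 gives 24 participants, 8 or more successes, 20% against 40%, and significance level 0.10. Exact binomial:

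- P(X ≥ 8 | n = 24, p = 0.20) = 0.089
- P(X ≥ 8 | n = 24, p = 0.40) = 0.808

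The 0.10 is reproduced as a ceiling. A cut-off of 7 would give 0.189.

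**3. Number of draws.** Cycle 1 Day 15 plus Day 1 of Cycles 2–12 gives 1 + 11 = 12. This is a maximum, because treatment ends at progression or clinical relapse (8.1). Section 1.3.5.2 reports a median time to progression of 5.1 months for carfilzomib alone in relapsed and refractory disease. That is a different regimen, but it suggests 5 or 6 draws: Day 1 of Cycle 6 is day 141.

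**4. Illustration, one value sufficient.** Three inputs are assumptions, not in the documents: m participants on this route (1 to 5), chance r per draw that a non-responder shows a qualifying fall (1–5%), and independent draws.

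- False partial response over k draws: f = 1 − (1 − r)^k
- Success probability on this route at a 20% true rate: 0.20 + 0.80f
- P(go) = P(Bin(24 − m, 0.20) + Bin(m, 0.20 + 0.80f) ≥ 8)

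| k | r | f | P(go), m = 1 | m = 2 | m = 5 |
|---|---|---|---|---|---|
| 5 | 1% | 0.049 | 0.093 | 0.096 | 0.107 |
| 5 | 2% | 0.096 | 0.096 | 0.103 | 0.127 |
| 6 | 2% | 0.114 | 0.097 | 0.106 | 0.134 |
| 12 | 2% | 0.215 | 0.104 | 0.121 | 0.182 |
| 12 | 5% | 0.460 | 0.122 | 0.162 | 0.329 |

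**5. The same illustration with two values at least six weeks apart.** Take k = 12 and r = 2%. A false response is avoided in three cases:

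- no draw qualifies: 0.98^12 = 0.7847
- exactly one qualifies: 12 × 0.02 × 0.98^11 = 0.1922
- exactly two adjacent draws qualify (11 pairs, 14 or 28 days apart): 11 × 0.02² × 0.98^10 = 0.0036

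So f = 1 − 0.9805 = 0.0195. The success probability on this route is 0.20 + 0.80 × 0.0195 = 0.216, and P(go) with m = 5 is 0.096, against 0.182 with one value.

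**6. The other phase II rule.** Section 5.3 (and the Schema) gives 17 participants and calls the regimen ineffective at 5 or fewer successes. P(X ≥ 6 | n = 17, p = 0.20) = 0.106. That is above 0.10 before any false response is counted. The conflict between 17 and 24 is a separate matter.

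**The case against.** **Silence is not a rule.** Section 9.5 never says that one light-chain value is enough. An assessor could hold that only the analyte is exchanged and that the repeat requirement carries over, since section 15.1 speaks of confirmed responses. This stands in part: the defensible claim is that no repeat is stated, and that the literal reading needs none. It does not remove the problem, because section 15.1 defines confirmed without any repeat and section 9.8 shows the same omission.

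**The false-positive rate roughly doubles.** A reader might infer this from the row with 0.182. The documents do not support it. That figure needs five participants on the route, the full 12 draws in non-responders and independent draws; none of the subgroup size, the per-draw rate or independence is given.

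**A safeguard already exists.** The bullet also requires an absolute fall of at least 10 mg/dl, and entry by light chains asks for a difference of 10 mg/dl (3.1.1). With a baseline difference below 20 mg/dl the fall must therefore exceed 50%; at 12 mg/dl, for instance, 10/12 = 83% is needed. The illustration ignores this, so it errs high. A participant with a plasmacytoma must also still meet the six-week condition. Both points stand.

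**The marrow substitute has the same gap.** Its bullet, a 50% "reduction in plasma cells is required in place of monoclonal protein provided that baseline bone marrow plasma cell percentage was" at least 30%, also states no repeat. A reader might extend the point to it. The repeated-draw mechanism does not reach that far: section 10.0 ties on-study marrow to confirming complete or stringent complete response or to clinical need, with an optional end-of-study sample. No size can be put on it, and re-checking serum, urine and light chains would not confirm the response, because those markers are unmeasurable on that route.

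**Conclusion.** The point holds for the light-chain route. As worded, sections 9.5 and 15.1 together let a single light-chain fall count as a confirmed partial response, while serum and urine responses need two determinations six weeks apart. Confidence in this reading of the text is high.

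The size is illustrative only. For the 24-participant rule at a 20% true rate, the error moves from 0.089 to somewhere between about 0.09 and 0.33 over the whole assumed range. It is about 0.10 to 0.13 for two to five participants with 5 or 6 draws at 2%. The absolute-fall condition would pull these figures down. With few such participants the error can stay below the stated 0.10. The inconsistency should be corrected because it sits in the primary endpoint and costs little to remove; there is no demonstrated large inflation.

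**What to change.** In section 9.5, add to the light-chain bullet the wording already used for M-protein: "for at least two determinations performed a minimum of six weeks apart". No change to the marrow bullet is proposed.

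No new sampling is needed. Light chains are drawn on Day 1 of every 28-day cycle, so Day 1 draws two cycles apart (56 days) satisfy six weeks, and Cycle 1 Day 15 with Cycle 3 Day 1 (day 15 to day 57, 42 days) just does.

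The cost is a small one. A few participants who leave within six weeks of a first qualifying fall, or before the next scheduled draw that meets the interval, will no longer count as responders. That already happens on the M-protein route.
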